## 5.2. Exclusion Criteria

A subject will not be eligible for inclusion in this study if any of the following criteria apply:

1. Primary malignancy of the central nervous system or malignancies related to human immunodeficiency virus (HIV) or solid organ transplant.
2. Recent prior therapy, defined as follows:

- a. Any investigational or Food and Drug Administration (FDA)-approved anti-cancer drug within 14 days or 5 half-lives, whichever is longer, prior to the first dose of GSK2820151. Note that an investigational drug is defined as a drug without an approved oncologic indication
  - b. Any radiotherapy, chemotherapy, targeted therapy or immunotherapy within 14 days or major surgery within 28 days or anti-neoplastic antibody or nitrosoureas/mitomycin C within 42 days prior to the first dose of GSK2820151.
  - c. Anti-androgen (e.g., bicalutamide) therapies for prostate cancer,, must be stopped 4 weeks prior to the first dose of GSK2820151. Second-line hormone therapies such as enzalutamide, abiraterone, or orteronel should be stopped 2 weeks prior to enrolment. Subjects with prostate cancer should remain on luteinizing hormone releasing hormone (LHRH) agonists or antagonists. Subjects with prostate cancer may also remain on low-dose prednisone or prednisolone (up to 10 mg/day) and still be eligible for this study.
  - d. In addition, any therapy-related toxicity must have resolved to Grade 1 or less, with the exception of alopecia (acceptable at any Grade) and peripheral neuropathy (which must be Grade 2 or less prior to enrollment).
3. Therapeutic anticoagulation (e.g., warfarin, heparin) must be discontinued 7 days prior to the first dose of GSK2820151 and coagulation parameters must be normalized prior to the first dose of GSK2820151. Low (prophylactic) dose low molecular weight heparin (LMWH) is permitted. In addition, INR must be monitored in accordance with local institutional practices.
  4. Current use of a prohibited medication or planned use of any forbidden medications during treatment with GSK2820151 (see Section 7.1.2 for the list of medications).

**NOTE:** Aspirin up to 100mg PO daily is allowed. Concurrent use of non-steroidal anti-inflammatory drugs (NSAIDs) will be excluded except for cases where NSAIDs provide benefit over other analgesics (see Section 7.1.2 for details).

5. Evidence of severe or uncontrolled systemic diseases (e.g., unstable or uncompensated respiratory, hepatic, renal, cardiac disease, or clinically significant bleeding episodes). Any serious and/or unstable pre-existing medical (aside from malignancy), psychiatric disorder, or other conditions that could interfere with subject's safety, obtaining informed consent or compliance to the study procedures, in the opinion of the Investigator.
6. Symptomatic or untreated leptomeningeal or brain metastases or spinal cord compression.

**NOTE:** Subjects previously treated for these conditions that have had stable central nervous system (CNS) disease (verified with consecutive imaging studies) for >1months, are asymptomatic and off corticosteroids, or are on stable dose of corticosteroids for at least 1 month prior to study Day 1 are permitted. Stability of brain metastases must be confirmed with imaging. Subject treated with gamma knife therapy can be enrolled 2 weeks post-procedure as long as there are no post-

procedure complications/stable. In addition, subjects treated or currently taking enzyme-inducing anticonvulsant (EIA) are allowed on study.

7. Cardiac abnormalities as evidenced by any of the following:
  - History of or current “untreated” clinically significant uncontrolled arrhythmias.
  - Clinically significant conduction abnormalities or arrhythmias
  - Presence of cardiac pacemaker
  - History or evidence of current  $\geq$ Class II congestive heart failure as defined by New York Heart Association (NYHA).
  - History of acute coronary syndromes (including unstable angina and myocardial infarction), coronary angioplasty, or stenting within the past 3 months. Subjects with a history of stent placement requiring ongoing antithrombotic therapy (e.g., clopidogrel, prasugrel) will not be permitted to enroll.
8. Following electrocardiogram (ECG) finding:
  - Baseline corrected QT (Fridericia’s formula) interval (QTcF)  $\geq$ 450 msec

**NOTE:** Any clinically significant ECG assessments should be reviewed by the site cardiologist prior to study entry.
9. Any of the following liver findings:
  - ALT  $>$ 2.5xULN
  - ALT  $>$  5xULN with liver metastases/tumor infiltration
  - Bilirubin  $>$ 1.5xULN (isolated bilirubin  $>$ 1.5xULN is acceptable if bilirubin is fractionated and direct bilirubin  $<$ 35%).
  - Current active liver or biliary disease (with the exception of Gilbert’s syndrome or asymptomatic gallstones, liver metastases or otherwise stable chronic liver disease per investigator assessment).

**NOTE:** Stable chronic liver disease should generally be defined by the absence of ascites, encephalopathy, coagulopathy, hypoalbuminaemia, esophageal or gastric varices, persistent jaundice or cirrhosis
10. Presence of hepatitis B surface antigen (HBsAg) or positive hepatitis C antibody test result at screening or within 3 months prior to first dose of study treatment. History of known HIV infection.

**NOTE:** Subjects with positive Hepatitis C antibody due to prior resolved disease can be enrolled only if a confirmatory negative Hepatitis C RNA polymerase chain reaction (PCR) is obtained.
11. Any serious known immediate or delayed hypersensitivity reaction(s) to GSK2820151 or idiosyncrasy to drugs chemically related to the investigational drug.

12. Hemoptysis > 1 teaspoon in 24 hours within the last 28 days.
13. Subjects with a history of known bleeding disorder(s) or history of clinical significant hemorrhage ( e.g., gastrointestinal, neurologic) within the last 6 months.
14. Any clinically significant gastrointestinal (GI) abnormalities that may alter absorption such as malabsorption syndrome or major resection of the stomach and/or bowels.

### **5.3. Screening/Baseline/Run-in Failures**

Screen failures are defined as subjects who consent to participate in the clinical trial but are never subsequently dosed with study medication. In order to ensure transparent reporting of screen failure subjects, meet the Consolidated Standards of Reporting Trials (CONSORT) publishing requirements, and respond to queries from Regulatory authorities, a minimal set of screen failure information is required including Demography, Screen Failure details, Eligibility Criteria, and any Serious Adverse Events.

### **5.4. Withdrawal/Stopping Criteria**

Subjects will receive study treatment until disease progression, death or unacceptable adverse event, including meeting stopping criteria for liver chemistry, hematologic/non-hematologic toxicity, QTc prolongation, raised Troponin level as defined in Section 14.7.1 or left ventricular ejection fraction (LVEF)/valvular dysfunction as defined in Section 5.4.1 through Section 5.4.5. After disease progression, subjects may be allowed to continue treatment with study drug if the Investigator strongly believes, and the GSK Medical Monitor concurs, that the subject could continue to receive benefit (for example in cases of an isolated new lesion, with the majority of the disease still under control).

In addition study treatment may be permanently discontinued for any of the following reasons:

- deviation(s) from the protocol
- request of the subject or proxy
- investigator's discretion
- subject is lost to follow-up
- study is closed or terminated.

The primary reason study treatment was permanently discontinued must be documented in the subject's medical records and electronic case report form (eCRF).

If the subject voluntarily discontinues from treatment due to toxicity, 'adverse event' will be recorded as the primary reason for permanent discontinuation on the eCRF.

Once a subject has permanently discontinued from study treatment, the subject will not be allowed to be retreated.

All subjects who discontinue from study treatment will have safety assessments at the time of discontinuation and during post study treatment follow-up as specified in Time and Events Tables (see Section 8.1).

All subjects who permanently discontinue study treatment for any reason will be followed for survival and new anti-cancer therapy (including radiotherapy) every 6 months until death, termination of the study by the sponsor, or until the subject has been followed for 2 years. Disease assessment will be collected for subjects who discontinue study medication due to any reason other than progression. If subjects are unable or unwilling to attend clinic visits during follow-up, contact to assess survival may be made via another form of communication (e.g., telephone, email, etc.).

The following actions must be taken in relation to a subject who fails to attend the clinic for a required study visit:

- The site must attempt to contact the subject and re-schedule the missed visit as soon as possible.
- The site must counsel the subject on the importance of maintaining the assigned visit schedule and ascertain whether or not the subject wishes to and/or should continue in the study.
- In cases where the subject is deemed ‘lost to follow up’, the investigator or designee must make every effort to regain contact with the subject (where possible, 3 telephone calls and if necessary a certified letter to the subject’s last known mailing address or local equivalent methods). These contact attempts should be documented in the subject’s medical record.
- Should the subject continue to be unreachable, only then will he/she be considered to have withdrawn from the study with a primary reason of “Lost to Follow-up”.

A subject may withdraw from study treatment at any time at his/her own request, or may be withdrawn at any time at the discretion of the investigator for safety, behavioral or administrative reasons. If a subject withdraws from the study, he/she may request destruction of any samples taken, and the investigator must document this in the site study records.

[figure not shown]
#### **5.4.1. Liver Chemistry Stopping Criteria**

Liver chemistry stopping and increased monitoring criteria have been designed to assure subject safety and evaluate liver event etiology (in alignment with the FDA premarketing clinical liver safety guidance):

<http://www.fda.gov/downloads/Drugs/GuidanceComplianceRegulatoryInformation/Guidances/UCM174090.pdf>.

[figure not shown]
See [Figure 3](#) and [Figure 4](#) for liver stopping criteria for subjects without and with liver metastases, respectively.

**Figure 3 Phase I/II Liver Chemistry Stopping and Increased Monitoring Algorithm for Subjects WITH entry criteria ALT  $\leq$ 2.5xULN**

Liver Safety Required Actions and Follow up Assessments Section can be found in [Appendix 3](#).

**Figure 4 Phase I/II Liver Chemistry Stopping and Increased Monitoring Algorithm including Subjects WITH documented liver metastases/tumor infiltration at baseline AND entry criteria ALT>2.5xULN but ≤5xULN**

Liver Safety Required Actions and Follow up Assessments Section can be found in [Appendix 3](#).

#### 5.4.1.1. Study Treatment Restart or Rechallenge

If subject meets liver chemistry stopping criteria do not restart/rechallenge subject with study treatment unless:

- GSK Medical Governance approval is granted
- Ethics and/or institutional review board (IRB) approval is obtained, if required, and
- Separate consent for treatment restart/rechallenge is signed by the subject

Refer to [Appendix 4](#) for full guidance.

#### 5.4.2. QTc Stopping Criteria

If a subject meets the corrected QT (QTc) interval duration criteria below, study treatment(s) will be withheld.

- QTcF interval  $\geq$  500 msec OR interval increase from baseline  $\geq$  60 msec: GSK2820151 will be discontinued unless the benefits of therapy outweigh the risk of rechallenge in the opinion of the investigator, the GSK Medical Monitor, as well as the GSK medical governance. In this situation, rechallenge may be permitted (see [Appendix 7](#) for rechallenge guidelines).

**NOTE:** QT interval duration criteria should be based on the average QTc value of triplicate electrocardiograms (ECGs) to include manual over-read. For example, if an ECG demonstrates a prolonged QT interval, obtain 2 additional ECGs over a brief period (e.g., within approximately 10 minutes of the abnormal ECG, if possible, and approximately 10 minutes apart from each other), and then use the averaged QTc values of the 3 ECGs to determine whether the subjects should have study treatment discontinued.

The QTc is the QT interval corrected for heart rate according to Fridericia's formula (QTcF).

- For eligibility and withdrawal, QTcF will be used for all subjects.
- For purposes of data analysis, QTcF will be used.

#### 5.4.3. LVEF Stopping Criteria

Echocardiography must be performed at Screening, Week 5 Day 1, Week 9 Day 1, and every 8 week thereafter and at the post-treatment follow-up visit as outlined in the Time and Events Table (Section 8.1). Subjects who have an asymptomatic, absolute decrease of  $>10\%$  in left ventricular ejection fraction (LVEF) compared with baseline and the ejection fraction is below the institution's lower limit of normal (LLN) should temporarily discontinue GSK2820151 and have a repeat evaluation of LVEF within 1 week. Echocardiogram (ECHO) should be repeated every 1 to 2 weeks for 4 weeks or until LVEF recovery to above institutional LLN and within 10% of baseline.

- If the LVEF recovers (defined as  $\geq$ LLN and absolute decrease  $\leq 10\%$  compared with baseline) at any time during the next 4 weeks, after consultation with and approval from the GSK Medical Monitor, the subject may be restarted on GSK2820151 at a reduced dose. For such subjects, monitoring of LVEF will be performed 2 and 4 weeks after rechallenge, and every 4 weeks thereafter for 16 weeks and then per protocol.
- If repeat LVEF does not recover within 4 weeks, treatment with GSK2820151 should be permanently discontinued. Ejection fraction should be monitored every 4 weeks for a total of 16 weeks or until resolution.

Subjects with Grade 3 or 4 (symptomatic) left ventricular systolic dysfunction must discontinue treatment with GSK2820151. Ejection fraction should be monitored every

4 weeks for a total of 16 weeks or until resolution. If recovery occurs (LVEF >institutional LLN and symptom resolution) within 4 weeks, treatment with GSK2820151 may be restarted at a reduced dose in consultation with the GSK Medical Monitor.

Copies of all ECHOs and cardiology consultations performed on subjects who experience a >10% decrease in LVEF from baseline and whose cardiac ejection fraction is <institution's LLN will be required by GSK for review. Instructions for submitting qualifying ECHOs are provided in the Laboratory Manual.

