## 14.7. Appendix 7: Guidelines for Management of Toxicity

The following dose modification criteria should provide guidance for, but not act as a replacement for sound clinical judgment. The investigator should use clinical judgment to determine which drug may be contributing to the toxicity necessitating dose adjustment, and make the appropriate change for that drug. Dose modifications should be made after discussion with the GSK medical monitor.

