LVEF	Ejection fraction below the institution's lower limit of normal (LLN)  AND  An asymptomatic, absolute decrease of >10% in LVEF compared to baseline	Withhold GSK2820151 and repeat evaluation of LVEF within 2 weeks  If LVEF recovers (defined as $\geq$ LLN and absolute decrease $\leq$ 10% compared to baseline) at any time during the next 4 weeks, after consultation and approval of the GSK medical monitor, the subject may be restarted on investigational drug(s) at a reduced dose. Monitoring to be performed at 2 and 4 weeks after restarting investigational drug(s) and then per protocol specifications.  If LVEF does not recover within 4 weeks, permanently discontinue investigational drug(s). Evaluation by a cardiologist will be conducted. Ejection fraction should continue to be monitored at 2 weeks, 4 weeks and every 4 weeks until 16 weeks or resolution, whichever is longer.
	Grade 3 or 4	Permanently discontinue GSK2820151. Evaluation by a cardiologist will be conducted. Ejection fraction should be monitored at 2 weeks, 4 weeks and then every 4 weeks until 16 weeks or resolution, whichever is longer.
Liver		Refer to procedures outlined in Appendix 3: Liver Safety Required Actions and Follow up Assessments
Hypo- and Hyperglycemia  Note: for management purposes, refer to mild, moderate and severe intensity criteria; however for CRF reporting use NCI-CTCAE version v4.03 Grade 1-5	Fasting blood glucose >150 mg/dL to 250 mg/dL (Mild hyperglycemia)	
 
Monitor fasting and preprandial glucose.
 
If persistent over 2 repeats over 3-4 weeks, consult Diabetologist and consider starting metformin
 

	Any blood glucose >250 mg/dL (Moderate to Severe hyperglycemia)	
 
Withhold GSK2820151 and instruct subject to notify investigator immediately. 
 
Monitor for ketoacidosis as clinically indicated.
 
If subject has evidence of ketoacidosis, initiate prompt therapy. Antihyperglycemic therapy with insulin is preferred. Consult Diabetologist/Endocrinologist . Careful monitoring should be performed to control for rebound hypoglycemia as effect of investigational product(s) resolve.
 
 
 
May consider restarting GSK2820151 at a reduced dose or dose level pre-event based on discussion with GSK Medical monitor.
 

Toxicity	Dose Adjustment/Stopping Criteria	Management Guidelines

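### Section 5.4.3 permits a restart after recovered Grade 3–4 LV dysfunction that Table 12 rules out, and no text says which governs

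*Protocol*

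**What the plan says.** Protocol Section 5.4.3 requires subjects with Grade 3 or 4 (symptomatic) LV systolic dysfunction to discontinue, without using the word permanently, and has ejection fraction monitored every 4 weeks for 16 weeks in all or until it resolves. It then opens a way back: "If recovery occurs (LVEF >institutional LLN and symptom resolution) within 4 weeks", the sentence continues, "treatment with GSK2820151 may be restarted at a reduced dose in consultation with the GSK Medical Monitor".

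The LVEF entry for Grade 3 or 4 in Table 12 reads "Permanently discontinue GSK2820151. Evaluation by a cardiologist will be conducted". It adds ejection fraction checks at 2 weeks, 4 weeks and then every 4 weeks until 16 weeks or resolution, whichever is longer. It has no recovery clause.

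Section 5.4 states: "Once a subject has permanently discontinued from study treatment, the subject will not be allowed to be retreated". The same section says where the stopping criteria are to be found: "raised Troponin level as defined in Section 14.7.1 or left ventricular ejection fraction (LVEF)/valvular dysfunction as defined in Section 5.4.1 through Section 5.4.5". The cardiovascular row of the risk table in Section 4.6.1, however, sends the reader to Section 14.7.1 for the stopping and modification criteria for cardiac events. Appendix 7, which holds Table 12, opens with "The following dose modification criteria should provide guidance for, but not act as a replacement for sound clinical judgment" and asks that dose changes follow discussion with the GSK Medical Monitor.

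**The concern.** The two places give incompatible instructions for the same subject in a first-in-human study that already treats cardiac toxicity as a leading risk. An investigator working from Section 5.4.3 may propose a reduced-dose restart. One working from Table 12 would regard the subject as permanently off drug and, under Section 5.4, not open to retreatment. What is at stake is re-exposure after a severe cardiac event on terms that depend on which page is read, and that are less demanding than the terms for a milder event. The SAP lists all protocol deviations, so it would also be unclear whether such a restart belongs in that listing.

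**Working it through.** No arithmetic applies to the main conflict, and the plan states no figure to reproduce. The check is a comparison of current texts.

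**Step 1. Same subject, two rules.** Take Grade 3 or 4 LV dysfunction with LVEF above the institutional lower limit of normal (LLN) and symptoms resolved within 4 weeks.

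- Section 5.4.3: reduced-dose restart permitted, in consultation with the Medical Monitor.
- Table 12: permanent discontinuation, hence no retreatment under Section 5.4.

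Table 12 omits the word symptomatic but covers the same grades.

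**Step 2. Does anything settle precedence?** Section 5.4 points LVEF to Sections 5.4.1–5.4.5. Section 4.6.1 points cardiac events to Section 14.7.1. Appendix 7 calls itself guidance, but the row is an unqualified instruction. Nor is silence in Table 12 obviously shorthand, because the table writes restart routes out where they are meant: QTcF (six conditions), asymptomatic LVEF decline and Grade 3 pneumonitis. The original protocol, reproduced in the same file, holds the same pair of rules. Amendment 4 reworked the LVEF rows of Table 12 and left the Section 5.4.3 sentence in place. Nothing reconciles them.

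**Step 3. The gate within Section 5.4.3.**

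| Element | Asymptomatic decline | Grade 3–4 symptomatic |
|---|---|---|
| Medical Monitor | consultation and approval | consultation |
| LVEF against LLN | at or above | above |
| LVEF against baseline | absolute decrease of 10% or less | none |
| Symptoms | not applicable | must have resolved |
| LVEF checks after rechallenge | 2 and 4 weeks, then every 4 weeks for 16 weeks | none stated |

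Write B for baseline LVEF and L for the LLN, both in percentage points. The asymptomatic route needs LVEF of at least the larger of L and B − 10. The Grade 3–4 route needs only LVEF above L. If B exceeds L + 10, any value above L but below B − 10 passes the LVEF test after the severe event and fails it after the mild one.

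**Step 4. How unusual is consultation alone?** Sections 5.4.1.1–5.4.4 hold six restart routes, counting the liver rule once:

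1. Liver: proceeds only if "GSK Medical Governance approval is granted".
2. QTc: needs the opinion of the investigator and of "the GSK Medical Monitor, as well as the GSK medical governance"; Table 12 makes governance approval one of its six conditions.
3. Asymptomatic LVEF decline: Medical Monitor approval.
4. Grade 3–4 LV dysfunction: consultation only.
5. Grade 2 valvular toxicity: Medical Monitor approval.
6. Grade 3–4 valvular toxicity: Medical Monitor approval.

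So 5 of 6 carry an approval step, if Table 12 is read with Section 5.4.2 for QTc, and 1 of 6 does not.

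**The case against.** The best defence is that Section 5.4.3 governs. Section 5.4 names Sections 5.4.1–5.4.5 for LVEF while sending troponin to Section 14.7.1, Appendix 7 describes itself as guidance, and the retreatment bar applies only once discontinuation is permanent, which Section 5.4.3 does not say. That is a reasonable inference and it limits the weight of the retreatment bar: the bar bites only if Table 12 applies. It does not remove the conflict, because Section 4.6.1 points the other way and a stopping rule should not have to be inferred.

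A second defence is that no site restarts on its own reading. This stands in part. Section 5.4.3 requires the Medical Monitor to be consulted, and Appendix 7 asks for discussion before dose changes. Recovery of LVEF and symptoms, a reduced dose, sponsor review of qualifying echocardiograms and ongoing Safety Review Team review also lower the risk. A reader might picture sites restarting subjects unsupervised; the text does not support that. What is missing is a requirement for approval before the restart.

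A reader might also infer from the 5-of-6 count that this is the weakest restart gate in the protocol. It is not. Table 12 asks only for discussion with the Medical Monitor after an asymptomatic repeat troponin elevation, Grade 3–4 fever, Grade 4 thrombocytopenia and Grade 3 pneumonitis, and its row for mucositis of Grade 3 or worse names no Medical Monitor step. The comparison that holds is the one inside Section 5.4.3, with the milder LVEF event.

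**Conclusion.** The inconsistency is real and should be corrected. Two current passages give opposite answers on restart after Grade 3–4 LV dysfunction that recovers within 4 weeks, and the protocol does not say which prevails. Within Section 5.4.3 the severe event also has the looser gate on three counts: approval, comparison with baseline and monitoring after rechallenge. It is stricter only in requiring symptom resolution and in asking for LVEF strictly above LLN.

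The size is limited to one event type. The documents give no expected frequency and report no occurrence, and the SAP records termination with 5 subjects enrolled, so the practical reach in this study is small. A reader might suppose that the conflict disturbs dose finding. It does not: no DLT count, MTD or statistical figure is affected. The conclusion assumes that the absolute LVEF decrease is measured in percentage points and that Table 12's grades describe the same event as Section 5.4.3.

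**What to change.** In Section 5.4.3, delete the Grade 3–4 restart sentence, state that these subjects must permanently discontinue, and take over Table 12's cardiologist evaluation and follow-up at 2 weeks, 4 weeks and then every 4 weeks until 16 weeks or resolution, whichever is longer.

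If the sponsor does intend rechallenge, write one route in both Section 5.4.3 and the Table 12 row: Medical Monitor approval; LVEF at or above LLN and within 10 points of baseline, with symptoms resolved; and the LVEF schedule that Section 5.4.3 already uses after restart in the asymptomatic case.

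The protocol should not simply declare that Section 5.4.3 overrides Table 12. That would weaken the table's cardiologist evaluation, 2-week check and longer-of-two follow-up rule, and would clash with the pointer in Section 4.6.1.

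The first option costs wording only, since Table 12 already requires those assessments. The second adds wording in two places and LVEF checks for any subject who is rechallenged.
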